5.6.3.2. Other Safety Parameters

5.6.3.2.1. Columbia Suicide Severity Rating Scale (C-SSRS)

The C-SSRS is a low-burden measure of the spectrum of suicidal ideation and behavior that was developed to assess severity and track suicidal events through any intervention (Posner 2007). It is a clinical interview providing a summary of both suicidal ideation and behavior that can be administered during any evaluation or risk assessment to identify the level and type of suicidality present. The C-SSRS has been used frequently in clinical studies, and is a validated, standard measure for suicidal ideation assessment. Using the C-SSRS, the outcomes will be categorized using the scoring for the 11 categories:

Suicida	uicidal Ideation (1-5)		
1	Wish to be dead		
2	Non-specific active suicidal thoughts		
3	Active suicidal ideation with any methods (not plan) without intent to act		
4	Active suicidal ideation with some intent to act, without specific plan		
5	Active suicidal ideation with specific plan and intent		
Suicida	Suicidal Behavior (6-10)		
6	Preparatory acts or behavior		
7	Aborted attempt		
8	Interrupted attempt		

9	Actual attempt		
10	Suicide		
Non-su	Non-suicidal self-injurious behavior (11)		
11	Non-suicidal self-injurious behavior		

At each time point, an event of suicidal ideation or behavior will be assigned a score of 1 to 10 based on the maximum response for the C-SSRS at that visit. If there is no event of suicidal ideation or behavior, a score of 0 will be assigned (0="no suicidal ideation or behavior that can be assessed on the basis of C-SSRS"). A participant with an event of non-suicidal self-injurious behavior only will not be considered as having suicidal ideation or behavior, therefore a score of 0 will be assigned. However, an additional score of 11 will be assigned to summarize any participants with an event of non-suicidal self-injurious behavior.

Shifts from the baseline to the maximum postbaseline score pertaining to suicidal ideation or suicidal behavior (i.e., scores 1 to 10) will be summarized by study intervention for each phase.

The maximum score (of scores 0 to 10) assigned to each participant will be grouped into one of three broad categories: No suicidal ideation or behavior (0), Suicidal ideation (1-5), Suicidal behavior (6-10). Shifts from baseline to the maximum postbaseline category will be summarized by study intervention for each phase.

A frequency distribution of the scores for the 11 categories (0 to 10) will be provided by study intervention at each time point for each phase. In addition, the number and proportion of participants with non-suicidal self-injurious behavior (a score of 11) will be provided by study intervention at each time point for each phase.

5.7. Other Analyses

5.7.1. Definition of Subgroups

Subgroup	Definition
Sex	Male
	Female
	Undifferentiated
Race	White
	Black
	Other
Age Group	18-34 years
	35-54 years
	55-64 years
	≥ 65 years
Failed antidepressant	2
intervention history	3 or more
Number of major	1
depressive episodes to date,	2
including current episode	≥3
Baseline MADRS total	Yes
score (<=/>median)	No

Subgroup	Definition
Antidepressant status at	On-treatment
screening / entry	Off-treatment

5.7.2. Pharmacokinetics

PK analyses will be performed on the safety analysis set.

Descriptive statistics (N, mean, SD, median, range, CV (%) and IQ range) will be used to summarize plasma concentrations at each sampling time point for esketamine (and noresketamine if measured)

5.7.3. Quality Tolerance Limit

Quality Tolerance Limit (QTL) parameters and thresholds are defined and will be monitored in this study. QTL parameters will be summarized. More details are described in the Integrated Analytical Risk-Based Monitoring (iARBM) Plan.

5.8. Interim Analyses

Not applicable.

6. SUPPORTING DOCUMENTATION

6.1. Appendix 1 List of Abbreviations

AD antidepressant AE adverse event

ANCOVA analysis of covariance BMI body mass index BP Blood pressure

CGI-S Clinical Global Impression – Severity

CI confidence interval
CR Copy reference
CRF case report form
CSR Clinical Study Report

C-SSRS Columbia Suicide Severity Rating Scale

DB Double-blind

DSM-5 Diagnostic and Statistical Manual of Mental Disorders (5th edition)

eCRF electronic case report form FDA Food and Drug Administration

F/U Follow-up

ICH International Conference on Harmonisation
MADRS Montgomery-Asberg Depression Rating Scale

MAR missing at random

MCMC Markov Chain Monte Carlo MDD Major Depressive Disorder

MedDRA Medical Dictionary for Regulatory Activities

MI multiple imputation

MMRM Mixed-Effect Model for Repeated Measures

MNAR Missing not at random

OBS Observation
OL Open-label

PD pharmacodynamic(s)

PHQ-9 Patient Health Questionnaire - 9 Item

PK pharmacokinetic(s)
SAE serious adverse event
QTL Quality Tolerance Limits
SAP Statistical Analysis Plan
SD standard deviation
SE Standard error
SOC Standard of care

TEAE treatment-emergent adverse event TRD Treatment Resistant Depression WHO World Health Organization

WHO-DD World Health Organization Drug Dictionary

6.2. Appendix 2 Changes to Protocol-Planned Analyses

Not applicable

6.3. Appendix 3 Demographics and Baseline Characteristics

The number of participants in each analysis set will be summarized and listed by intervention group, combined active intervention group, and overall. In addition, the distribution of participants by site ID will be presented.

Table 8 presents a list of the demographic variables that will be summarized by intervention group, combined active intervention group, and overall for the full efficacy analysis set, safety analysis set and randomization list 2 analysis set.

Table 8: Demographic Variables

Continuous Variables	Summary Type
Age (years)	Descriptive statistics (N. maan
Weight (kg)	Descriptive statistics (N, mean,
Height (cm)	standard deviation [SD], median and range [minimum and maximum]).
Body Mass Index (BMI) (kg/m²)	range [imminum and maximum]).
Categorical Variables	
Age (18-34 years, 35-54 years, 55-64 years, and ≥65 years)	
Sex (male, female, undifferentiated)	
Race ^a (American Indian or Alaska Native, Asian, Black or African American,	Frequency distribution with the number
Native Hawaiian or other Pacific Islander, White, Multiple)	and percentage of participants in each
Ethnicity (Hispanic or Latino, not Hispanic or Latino)	category.
BMI (underweight <18.5 kg/m ² , normal 18.5-<25 kg/m ² , overweight	
$25 - 30 \text{ kg/m}^2$, obese $> = 30 \text{ kg/m}^2$)	
Antidepressant status at screening / entry (On-treatment, Off-treatment)	

If multiple race categories are indicated, the Race is recorded as 'Multiple'

A summary of the stratification factors will be provided by intervention arm.

Table 9 presents a list of the baseline disease characteristics variables that will be summarized by intervention group, combined active intervention group, and overall for the full efficacy analysis set, safety analysis set and randomization List 2 analysis set.

Table 9: Baseline Disease Characteristics

Continuous Variables	Summary Type	
Age (years) when diagnosed with MDD	Summary Type	
Duration (weeks) of current depressive episode	Descriptive statistics (N, mean,	
Baseline MADRS total score	standard deviation [SD], median and	
Baseline CGI-S score	range [minimum and maximum]).	
Baseline PHQ-9 total score		
Screening IDS-C ₃₀ total score		
Categorical Variables		
Baseline CGI-S score (Normal (not at all ill), Borderline mentally ill, Mildly ill,		
Moderately ill, Markedly ill, Severely ill, Among the most extremely ill patients)		
Screening C-SSRS lifetime (no event, suicidal ideation, suicidal behavior)		
Screening C-SSRS past 6 or 12-month (no event, suicidal ideation, suicidal		
behavior)	F	
Antidepressant treatment history (number of medications taken for at least 6 weeks	Frequency distribution with the number	
during the current episode as obtained in the MGH-ATRQ)	and percentage of participants in each	
Failed antidepressant intervention history (2, 3 or more)	category.	
Number of major depressive episodes to date, including current episode $(1, 2, \ge 3)$		
Family history of alcohol abuse (Yes, No)		
Family history of anxiety disorder (Yes, No)		
Family history of bipolar disorder (Yes, No)		
Family history of depression (Yes, No)		

Family history of schizophrenia (Yes, No)	
Family history of substance abuse (Yes, No)	

6.4. Appendix 4 Protocol Deviations and Quality Tolerance Limits (QTL)

In general, the following list of major protocol deviations may have the potential to impact participants' rights, safety or well-being, or the integrity and/or result of the clinical study. Participants with major protocol deviations will be identified prior to database lock and the participants with major protocol deviations will be summarized by category for the all randomized analysis set.

- Developed withdrawal criteria but not withdrawn
- Entered but did not satisfy criteria
- Received a disallowed concomitant treatment
- Received wrong treatment or incorrect dose
- Other

Number of participants not meeting inclusion criteria, or meeting exclusion criteria will be summarized by study intervention group for the all randomized analysis set.

Quality Tolerance Limit parameters and thresholds are defined and will be monitored in this study. QTL parameters will be summarized. More details are described in the Integrated Analytical Risk-Based Monitoring (iARBM) Plan.

6.5. Appendix 5 Prior and Concomitant Medications

Prior medications and concomitant medications will be coded using the World Health Organization Drug Dictionary (WHO-DD). Prior medications are defined as any therapy used before the day of first dose (partial or complete) of study intervention. Concomitant medications are defined as any therapy used on or after the same day as the first dose of study intervention, including those that started before and continue on after the first dose of study intervention.

Summaries of concomitant medications will be presented by base preferred term for the double-blind, open-label treatment/observation and follow-up phases for safety, open-label/observation and safety analysis sets, respectively. The proportion of participants who receive each concomitant medication will be summarized as well as the proportion of participants who receive at least 1 concomitant medication. In addition, concomitant medications of special interest will be summarized. These include antidepressant medications received prior to the first dose of study intervention. See Appendix 8 for list of medications in each category.

Prior medications and prior medications of special interest will be summarized by base preferred term.

6.6. Appendix 6 Medical History

Not applicable

6.7. Appendix 7 Adverse Events of Special Interest

Adverse events of special interest are defined as follows:

AE Special Interest Category	Preferred Term
Drug abuse, dependence and withdrawal Increased blood pressure	Aggression, Confusional state, Decreased activity, Dependence, Disorientation, Dissociation, Dissociative disorder, Dizziness, Drug use disorder, Drug abuse, Drug abuser, Drug dependence, Drug detoxification, Drug diversion, Drug rehabilitation, Drug tolerance, Drug tolerance increased, Drug withdrawal convulsions, Drug withdrawal headache, Drug withdrawal syndrome, Euphoric mood, Feeling abnormal, Feeling drunk, Feeling of relaxation, Hallucination, Hallucination auditory, Hallucination gustatory, Hallucination olfactory, Hallucination synesthetic, Hallucination tactile, Hallucination visual, Hallucinations mixed, Inappropriate affect, Mental impairment, Product tampering, Psychomotor hyperactivity, Psychotic disorder, Rebound effect, Somatic Hallucination, Somnolence, Substance abuser, Substance dependence, Substance use, Substance use disorder, Substance-induced mood disorder, Substance-induced psychotic disorder, Thinking abnormal, Withdrawal arrhythmia, Withdrawal syndrome Blood pressure increased, Blood pressure diastolic increased, Blood
increased blood pressure	pressure systolic increased, Hypertensive crisis, Hypertensive emergency, Hypertension
Increased heart rate	Heart rate increased, Tachycardia, Extrasystoles
Transient dizziness/vertigo	Dizziness, Dizziness exertional, Dizziness postural, Dizziness procedural, Procedural dizziness, Vertigo, Vertigo labyrinthine, Vertigo positional, Vertigo CNS origin
Impaired cognition	Cognitive disorder
Cystitis	Allergic cystitis, Chemical cystitis, Cystitis, Cystitis erosive, Cystitis haemorrhagic, Cystitis interstitial, Cystitis noninfective, Cystitis ulcerative, Cystitis-like symptom, Pollakiuria, Dysuria, Micturition urgency, Nocturia
Anxiety	Anticipatory anxiety, Anxiety, Anxiety disorder, Agitation, Fear, Feeling jittery, Irritability, Nervousness, Panic attack, Tension
Anticipated Dosing-related AEs	Anxiety, Anticipatory anxiety, Dissociation, Dizziness, Dizziness postural, Feeling abnormal, Feeling drunk, Nausea, Somnolence, Vertigo, Vomiting
Events potentially related to suicidality	Completed suicide, Depression suicidal, Intentional overdose, Intentional self-injury, Multiple drug overdose intentional, Poisoning deliberate, Self-injurious behavior, Self-injurious behaviour Self-injurious ideation, Suicidal behavior, Suicidal behaviour, Suicidal ideation, Suicidal attempt
Hepatic adverse events	Cholecystitis, Cholelithiasis, Hepatic steatosis, Hepatitis, Non-alcoholic steatohepatitis, Primary biliary cholangitis, Alanine aminotransferase increased, Aspartate aminotransferase increased, Blood bilirubin increased, Gamma-glutamyl transferase increased, Hepatic enzyme increased, Liver function test abnormal, Liver function test increased, Transaminases increased, Urine bilirubin increased, Urobilinogen urine increased
Events related to renal disorders	Cystitis, Pyelonephritis, Urethritis, Urinary tract infection, Blood creatinine increased, Blood urea increased, Blood urine present, Creatinine renal clearance increased, Protein urine present, Urine analysis abnormal, Urine leukocyte esterase positive, Bladder discomfort, Bladder irritation, Bladder outlet obstruction, Cystitis noninfective, Dysuria, Haematuria, Hypertonic bladder, Lower urinary tract symptoms, Micturition urgency, Nephrolithiasis, Nocturia, Pollakiuria, Polyuria, Proteinuria, Renal colic, Renal failure, Semenuria, Stress urinary incontinence, Ureterolithiasis, Urge incontinence, Urinary bladder polyp, Urinary hesitation, Urinary incontinence, Urinary retention

AE Special Interest Category	Preferred Term
Symptoms of dissociation	Dissociation[QX[2]
persisting beyond the typical ≤ 2	
hour post esketamine	
administration	
Delirium	Post-injection delirium sedation syndrome, Postoperative delirium,
	Delirium, Intensive care unit delirium
Psychosis	Acute psychosis, Affective disorder, Alcoholic psychosis, Bipolar I
	disorder, Epileptic psychosis, Hysterical psychosis, Mania, Parkinson's
	disease psychosis, Postictal psychosis, Psychosis postoperative, Psychotic
	disorder, Psychotic disorder due to a general medical condition, Reactive
	psychosis, Rebound psychosis, Schizoaffective disorder, Substance-
	induced psychotic disorder, Transient psychosis
Mania	Hypomania, Mania

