8.3.6. Adverse Events of Special Interest

Clinically relevant TEAEs of special interest will be examined separately grouped in the following categories:

- Suggestive of abuse potential (Aggression, Confusional state, Decreased activity, Dependence, Disorientation, Dissociation, Dissociative disorder, Dizziness, Drug abuse, Drug abuser, Drug dependence, Drug use disorder, Drug detoxification, Drug diversion, Drug rehabilitation, Drug tolerance, Drug tolerance increased, Drug withdrawal convulsions, Drug withdrawal headache, Drug withdrawal syndrome, Euphoric mood, Feeling abnormal, Feeling drunk, Feeling of relaxation, Hallucination, Hallucination, auditory, Hallucination, gustatory, Hallucination, olfactory, Hallucination, synaesthetic, Hallucination, tactile, Hallucination, visual, Hallucinations, mixed, Inappropriate affect, Mental impairment, Product tampering, Psychomotor hyperactivity, Psychotic disorder, Rebound effect, Somatic hallucination, Somnolence, Substance abuser, Substance dependence, Substance use, Substance use disorder, Substance-induced mood disorder, Substance-induced psychotic disorder, Thinking abnormal, Withdrawal arrhythmia, Withdrawal syndrome);
- Increased blood pressure (Blood pressure increased, Blood pressure diastolic increased, Blood pressure systolic increased, Hypertensive crisis, Hypertensive emergency, Hypertension);
- Increased heart rate (Heart rate increased, Tachycardia, Extrasystoles);
- Transient dizziness/vertigo (Dizziness, Dizziness exertional, Dizziness postural, Dizziness procedural, Procedural dizziness, Vertigo, Vertigo labyrinthine, Vertigo positional, Vertigo CNS origin);
- Impaired cognition (Cognitive disorder);
- Cystitis (Allergic cystitis, Chemical cystitis, Cystitis, Cystitis erosive, Cystitis haemorrhagic, Cystitis interstitial, Cystitis noninfective, Cystitis ulcerative, Cystitis-like symptom, Pollakiuria, Dysuria, Micturition urgency, Nocturia);
- Anxiety (Agitation, Anticipatory anxiety, Anxiety, Anxiety disorder, Fear, Feeling jittery, Irritability, Nervousness, Panic attack, Tension);
- Anticipated Dosing-related AEs (Anxiety, Anticipatory anxiety, Dissociation, Dizziness, Dizziness postural, Feeling abnormal, Feeling drunk, Nausea, Somnolence, Vertigo, Vomiting);

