- Suicidality (Completed suicide, Depression suicidal, Intentional overdose, Intentional self-injury, Multiple drug overdose intentional, Poisoning deliberate, Self-injurious behavior, Self-injurious ideation, Suicidal behavior, Suicidal ideation, Suicide attempt)

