		Added a new remission (PHQ-9	New criteria and analyses were
		<5) and response (≥50%	added to be consistent with the
		improvement) criteria based on	definition in phase 3 program

SAP Version	Approval Date	Change	Rationale
		PHQ-9 in Section 1.1 and Section	
		5.5.6 and 5.5.8	
		Added remission and response rates plot for the double-blind phase and open-label treatment or observation phase in Section 5.5.10	Provided figures for the existing tables for better visualization
		Added Antidepressant status at screening / entry (On-treatment, Off-treatment) to Table 8	Provided summary statistics for stratification factor
		Added two preferred terms "Self- injurious behaviour" and "Suicidal behaviour" to the AE of special interest category of "Events potentially related to suicidality" in Section 6.7	Provided a more comprehensive list of preferred terms for AEs of special interest categories.
		Remove "Clotiapine" from CM of special interest category of Typical Antipsychotics in Section 6.8	Provided a unique CM of special interest category to eliminate confusion

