5.6.2. Adverse Events

The verbatim terms used in the CRF by investigators to identify adverse events will be coded using the Medical Dictionary for Regulatory Activities (MedDRA). Any AE occurring at or after the initial administration of study intervention through the day of last dose is considered to be treatment emergent. If the event occurs on the day of the initial administration of study intervention, and either event time or time of administration are missing, then the event will be assumed to be treatment emergent. If the event date is recorded as partial or completely missing, then the event will be considered to be treatment emergent unless it is known to be prior to the first administration of study intervention based on partial onset date or resolution date. All reported treatment-emergent adverse events will be included in the analysis. For each adverse event, the number and percentage of participants who experience at least 1 occurrence of the given event will be summarized by intervention group.

Assignment of adverse events to double-blind, open-label treatment/observation or follow-up phase will be made based on the following rules:

Double-blind phase:

AEs will be assigned to the double-blind analysis phase as detailed below.

- For participants who did not continue to open-label treatment/observation phase or participants who chose to be observed only (receive SOC only) in the observation phase: double-blind phase start date/time ≤AE onset date/time ≤double-blind phase end date.
- For participants who received open-label esketamine nasal spray: double-blind phase start date /time ≤AE onset date/time <double-blind phase end date/time (ie, open-label phase start date/time)
 - AEs that occur on the last day of double-blind phase but AE onset time is missing will be assigned to the double-blind phase.

AEs that are assigned to the double-blind analysis phase as detailed below will be considered as treatment-emergent.

- For participants completed double-blind treatment: all the AEs in the double-blind treatment phase will be considered as treatment-emergent for the double-blind phase.
- For participants who discontinued double-blind treatment and double-blind phase at the same time, all the AEs in the double-blind treatment phase will be considered as treatment-emergent for the double-blind phase.

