- For participants who discontinued double-blind treatment but continued to be assessed until the end of double-blind phase (Day 28), AEs will be considered as treatment-emergent for the double-blind phase only if they satisfy the condition: double-blind phase start date /time ≤ AE onset date/time ≤ last day of double-blind treatment.

Open-label treatment phase:

- For participants who received open-label esketamine nasal spray, all AEs that are assigned to the open-label treatment phase will be considered as treatment-emergent if they satisfy the condition: open label treatment phase start date/time≤ AE onset date/time ≤ open label treatment phase end date.
 - AEs that occur on the last day of double-blind phase but AE onset time is after open-label dosing will be considered as treatment-emergent for the open-label treatment phase.

Observation phase:

• For participants who received SOC only in the observation phase, all AEs that are assigned to the observation phase will not be considered as treatment-emergent if they satisfy the condition: double-blind phase end date+1≤ AE onset date ≤ observation phase end date.

Follow-up phase:

• Any AEs that are assigned to the follow-up phase will not be considered as treatmentemergent. AEs during the follow-up phase should satisfy the condition: follow-up phase start date ≤AE onset date ≤follow-up phase end date.

Summary tables will be provided for adverse events by phase:

- AEs
- Serious AEs (SAEs)
- AEs leading to discontinuation of each study agent within a study intervention
- AEs by severity
- AEs by relationship to each study agent within a study intervention
- AEs of special interest

In addition to the summary tables, listings will be provided for participants who had:

- SAEs
- AEs leading to discontinuation of study intervention
- AEs of special interest

Incidence of other treatment-emergent adverse events of special interest will be summarized. See Appendix 7 for list of adverse events in each category.

The proportion of TEAEs occurring on dosing days and the proportion of TEAEs that occur on dosing days with same day resolution will be summarized. Duration and resolution time of severe TEAEs will also be summarized.

A listing of participants who died will be provided.

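### The SAP's special-interest suicidality row prints *Suicidal attempt* where the protocol lists *Suicide attempt*, so selecting on the printed terms would miss events coded *Suicide attempt*

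*SAP*

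**What the plan says.** Protocol Section 8.3.6 groups the adverse events of special interest into nine categories. The last is suicidality, with 11 terms ending "Suicidal behavior, Suicidal ideation, Suicide attempt".

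SAP Section 5.6.2 states that "The verbatim terms used in the CRF by investigators to identify adverse events will be coded using the Medical Dictionary for Regulatory Activities". It plans a summary and a participant listing of special-interest events and directs the reader to the appendix: "See Appendix 7 for list of adverse events in each category". Appendix 7 opens with "Adverse events of special interest are defined as follows" and sets the terms out under a column headed Preferred Term. Its suicidality row ends "Suicidal behavior, Suicidal behaviour, Suicidal ideation, Suicidal attempt".

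The SAP Version History records that version 4.0 added *Self-injurious behaviour* and *Suicidal behaviour* to this same row, with the rationale "Provided a more comprehensive list of preferred terms for AEs of special interest categories". SAP Appendix 2 declares no changes to the analyses planned in the protocol.

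**The concern.** Appendix 7 is an operative definition: it decides which coded events count towards each category. A row that lists ideation and behaviour but not the protocol's term for an attempt could produce a suicidality table from which attempts are missing.

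Potential effects on suicidal ideation and behaviour are a stated safety objective in both documents, and Protocol Section 8.2.5 notes that attempts are a recognised risk in this population. The protocol's background section reports suicide attempts in earlier esketamine studies, so the term is not a hypothetical one.

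**Working it through.** No sample size, power or alpha figure is involved. The check is an entry-by-entry comparison of Protocol 8.3.6 with the matching rows of SAP Appendix 7. Terms repeated across categories are counted each time. Two breaks in the extracted text are read in the SAP's favour: the missing comma between *Self-injurious behaviour* and *Self-injurious ideation* is treated as a separator, and the broken blood-pressure row is read as its six terms.

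**Suicidality row**

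| | Protocol 8.3.6 | SAP Appendix 7 |
|---|---|---|
| Number of terms | 11 | 13 |
| Only in this document | *Suicide attempt* | *Suicidal attempt*, *Self-injurious behaviour*, *Suicidal behaviour* |

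Shared terms: 11 − 1 = 10, and 13 − 3 = 10, so the counts agree. Two of the three SAP-only terms are the recorded version 4.0 additions. The third, *Suicidal attempt*, has no recorded explanation. An exact match of *Suicide attempt* against the SAP row returns nothing. With the last term replaced by *Suicide attempt*, all 11 protocol terms are found.

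**All nine protocol categories**

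| Category | Protocol entries | Not printed identically in the SAP |
|---|---|---|
| Abuse potential | 49 | 8 |
| Increased blood pressure | 6 | 0 |
| Increased heart rate | 3 | 0 |
| Dizziness/vertigo | 9 | 0 |
| Impaired cognition | 1 | 0 |
| Cystitis | 13 | 0 |
| Anxiety | 10 | 0 |
| Anticipated dosing-related | 11 | 0 |
| Suicidality | 11 | 1 |
| **Total** | **113** | **9** |

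Identical entries: 113 − 9 = 104.

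The eight abuse-potential differences are all hallucination terms. For seven of them the protocol prints "Hallucination, auditory, Hallucination, gustatory, Hallucination, olfactory, Hallucination, synaesthetic, Hallucination, tactile, Hallucination, visual, Hallucinations, mixed" and the SAP prints "Hallucination auditory, Hallucination gustatory, Hallucination olfactory, Hallucination synesthetic, Hallucination tactile, Hallucination visual, Hallucinations mixed". The eighth, *Somatic hallucination*, differs by one capital letter. If case and commas are ignored, 2 of the 9 remain: *synaesthetic*/*synesthetic*, which is a spelling variant, and *Suicide*/*Suicidal attempt*. The attempt term is the only one of the 113 that changes a word.

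**The case against.** The strongest reply is that this is a retyping slip that would do no harm in practice. Appendix 7 was loosely transcribed in other places: the abuse-potential category was renamed and the hallucination terms were repunctuated. The row's title, on events potentially related to suicidality, plainly covers an attempt. The version 4.0 edit was meant to widen the row, and no change from the protocol was declared. The protocol's own background narrative uses both wordings. A programmer working from the coding dictionary might well select the right term. The documents do not reproduce that dictionary, so they cannot show which wording it holds.

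There are also other reporting routes. Treatment-emergent attempts stay in the general AE tables. Serious ones appear in the SAE table and listing (SAP 5.6.2) and in narratives (Protocol 9.4.5). The C-SSRS summaries score an actual attempt as 9 (SAP 5.6.3.2.1). Participants with recent suicidal intent or behaviour are excluded, and earlier TRD studies reported suicidality-related events at about 1% to 5%, mostly ideation. Protocol 9.4.5 omits suicidality from its own recital of special-interest categories, although 8.3.6 includes it.

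Most of this stands, and it limits the weight of the point. A slip is the likeliest explanation, and actual loss of events is not established. It does not make the row correct. A list that defines an analysis should not depend on someone noticing that it departs from the protocol. The version 4.0 edit, which added alternative spellings as separate terms, shows that exact wording was treated as significant in this very row. Reporting the events elsewhere does not make the suicidality category complete.

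**Conclusion.** The row is wrong as written, and the point is minor. One of the protocol's 11 suicidality terms is not carried into the SAP definition. Events would be omitted only if MedDRA coding yields *Suicide attempt* and selection follows the printed terms; neither can be confirmed from the documents. Under those conditions such events are left out of one descriptive summary and its listing. No estimate of affected participants is possible, and there may be none. Nothing in the primary or key secondary analysis changes.

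**What to change.** Add *Suicide attempt* to the suicidality row of SAP Appendix 7, as in Protocol 8.3.6. Keeping *Suicidal attempt* beside it as a variant is harmless.

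Before the tables are produced, check every Appendix 7 term against the MedDRA version in use, including the eight hallucination terms that are printed differently from the protocol. Confirm at the same time that *Self-injurious behaviour* and *Self-injurious ideation* are separate entries; the missing comma may only be a PDF-reading artefact.

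The cost is one added term in one appendix row and a term check against the coding dictionary.
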